8.3.1 Baseline Data

Baseline and demographic characteristics will be summarized by standard descriptive statistics (including mean and standard deviation for continuous variables such as age and standard percentages for categorical variables such as gender).

8.3.2 Efficacy Analysis

8.3.2.1 Part 1

• Number of times the helmet deploys in normal controls (or dummies) falling from a standing position.

8.3.2.2 Part 2

- Number of days that subjects in the helmet group actually wore the helmet
- Compare the fraction of the time the device deployed during a seizure that resulted in a fall
- Compare the number of times the helmet deployed in a seizure vs. non-seizure event
- Compare seizures that trigger helmet deployment to those that do not trigger helmet deployment

8.3.3 Safety Analysis

All subjects entered into the study and randomized at the baseline visit will have detailed information collected on adverse device effects (ADE) for the overall study safety analysis.

8.3.3.1 Part 2

• N/A

8.3.3.2 Part 2

• Compare the rates of injury and post concussive syndromes in subjects where the helmet inflated during a seizure related fall to seizure related falls where the helmet did not inflate.

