3.2.2.2 Secondary Study Endpoints

- Rates of helmet deployment (per event) during seizures associated with falls, and rates of helmet deployment (per day of use) not associated with seizure.
- Qualitative description of any adverse events.
- Differences in Rivermead Post Concussive Scale, Seizure Questionnaire, injury-related medical records, and qualitative subject report between subjects following a seizure in which the helmet deployed, and seizures in which the helmet was either not being worn or did not deploy

4 Study Population and Duration of Participation

4.1 Part 1

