8.3 Statistical Methods

Part 2:

- Will compare rates of injury and post concussive syndrome in falls where the helmet was being worn versus falls where the helmet was not being worn.
- Descriptive statistics will be collected on the proportion of days that subjects assigned to wear the helmet actually wear the helmet
- Descriptive statistics will also be collected on rates of helmet deployment (per event) during seizures associated with falls, and rates of helmet deployment (per day of use) not associated with seizure
- Will compare rates of injury and post concussive syndrome in falls where the helmet was being worn and deployed versus falls where the helmet was either not being worn or did not deploy

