9.1 Definitions

9.1.1 Adverse Device Effects

An **adverse device effect (ADE)** is any untoward medical occurrence associated with the use of a device in humans.

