9.2 Recording of Adverse Device Effects and Adverse Events

The study investigator is ultimately responsible for the recording and reporting of AEs, ADEs, and unanticipated problems related to the research, which occur during the study. The study team will collect AE and ADE information from the start of the study (after consent is signed) until the last follow up visit.

At each contact with the subject, a member of the study team will seek information on AEs and ADEs by specific questioning and, as appropriate, by examination. Information on all AEs and ADEs will be recorded immediately in the source document. All clearly related signs, symptoms, and abnormal diagnostic procedures results should be recorded in the source document, though should be grouped under one diagnosis. These AEs and ADEs will be recorded on paper source documents and reviewed by the Principal Investigator and Sponsor designated pharmacovigilance lead (Medical Director).

All AEs and ADEs occurring during the study period will be recorded. The clinical course of each event will be followed until resolution, stabilization, or until it has been determined that the study intervention or participation is not the cause. SAEs and UADEs that are still ongoing at the end of the study period will be followed up to determine the final outcome. Any SAEs and UADEs that occur after the study period and is considered to be possibly related to the study intervention or study participation will be recorded and reported immediately.

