9.3 AE/ADE Assessment

The Sponsor-Investigator will determine relationship classification (definitely related, probably related, possibly related, unlikely or unrelated), expectedness (expected or unexpected), and seriousness (serious or non-serious as defined per protocol) of all AEs and ADEs. The relationship of each event will be followed up on until it has been determined that the event is definitely related or definitely not related to the device or participation on the study.

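### Apart from injury and post-concussive syndrome, the planned safety analysis rests on adverse device effects, so the no-helmet period supplies no background rate for other adverse events

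*Combined protocol and SAP*

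**What the plan says.** **Safety analysis.** Under 8.3.3, all randomised subjects "will have detailed information collected on adverse device effects (ADE) for the overall study safety analysis". Section 8.3.3.2 adds one comparison: "Compare the rates of injury and post concussive syndromes in subjects where the helmet inflated during a seizure related fall", set against seizure-related falls without inflation.

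**Definitions.** Section 9.1.1 defines an ADE as "any untoward medical occurrence associated with the use of a device in humans". Section 9.1.3 defines an AE without reference to the device and counts injuries as AEs.

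**Collection.** Section 9.2 states that "All AEs and ADEs occurring during the study period will be recorded", and that at each contact "a member of the study team will seek information on AEs and ADEs by specific questioning". It covers the time from consent to the last follow-up visit, so both periods are included. The procedure lists are narrower. Sections 3.1.2.3, 3.1.2.4, 6.2.1.3 and 6.2.1.5 name review or collection of ADEs only. The Table 2 row covers ADEs, unanticipated ADEs and unanticipated problems. The monthly contact in 7.10 covers seizure frequency, falls and time in the helmet.

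**Planned use of AEs in general.** The secondary endpoint in 3.2.2.2, repeated in 8.1.1.2, is "Qualitative description of any adverse events".

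**Comparison by helmet wear.** Section 8.3: "Will compare rates of injury and post concussive syndrome in falls where the helmet was being worn", against falls where it was not.

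**The concern.** The trial is titled as a safety pilot and randomises the order of a helmet and a no-helmet period. The no-helmet period shows how often a complaint arises without the device in the same people. An outcome that can arise only in connection with the device makes no use of that period.

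This matters for events that also happen without a helmet. Section 12.1.2 lists neck abrasions, temporary hearing impairment and collar discomfort as foreseeable device effects. At least the first two could plausibly occur in people who have frequent seizures and falls. If such events are counted only as ADEs, or described without a denominator, a reader cannot tell whether the helmet adds to them. The larger study that Section 2 hopes to plan would then have no background figure from this pilot.

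The difference between the procedure lists and 9.2 adds a practical risk. Staff who work from Table 2 may not ask subjects in the no-helmet period about AEs at all, and the data needed for a later comparison would be incomplete.

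**Working it through.** The plan gives no figure to reproduce: 8.2 is marked not applicable, and no AE rate, alpha or power is stated. The check is mainly a comparison of sections.

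**Step 1: which events have a planned helmet versus no-helmet comparison?**

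- *Injury and post-concussive syndrome:* yes, worn versus not worn, per fall (8.3). Section 8.3.3.2 adds inflated versus not inflated, which is not the randomised contrast.
- *ADEs:* named for the overall safety analysis (8.3.3). The definition in 9.1.1 leaves essentially none in the no-helmet period, so there is no comparison.
- *All other AEs:* recorded in both periods (9.2), but described qualitatively only (3.2.2.2, 8.1.1.2). No rate, denominator or split by period is planned.

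**Step 2: could the comparison be made from data already required?** Yes, if 9.2 is followed. Section 8.4 already defines an all-randomised population for comparisons of helmet with no helmet. The daily calendar (7.5) records helmet wearing.

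**Step 3: which denominators fit?** Under 5.2 a subject stays in a period until a helmet deployment and/or a seizure-related fall. Period length therefore varies between subjects and between periods, and counts need person-days beside them. Under 3.1 and 5.2 a subject without a seizure-related fall in 3 months becomes a screen failure, so fewer than 20 may enter the second period. The denominator for each period is the number who entered it.

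**Step 4: how precise would the table be?** The sample of about 20 is from 4.5.2. The event rates below are assumptions.

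- *No events of a given type in n subjects.* The one-sided 95% upper bound is 1 − 0.05^(1/n). For n = 20 it is 13.9%. The two-sided version, 1 − 0.025^(1/20), is 16.8%. If as few as 5 subjects entered a period (an assumed low end), the one-sided bound is 1 − 0.05^(1/5) = 45.1%.
- *Approximate power.* Treat the periods as independent groups of n = 20, two-sided 0.05, with p̄ the mean of p1 and p2: Φ{(|p1 − p2| − 1.96·√[2p̄(1 − p̄)/n]) / √[(p1(1 − p1) + p2(1 − p2))/n]}.
  - 10% versus 30%: Φ{(0.200 − 0.248)/0.122} ≈ 35%.
  - 10% versus 40%: Φ{(0.300 − 0.268)/0.128} ≈ 60%.
  - 10% versus 50%: Φ{(0.400 − 0.284)/0.130} ≈ 81%.
- *Exact paired test.* With d discordant subjects all in one direction, p = 2 × 0.5^d. For d = 5, p = 0.0625; for d = 6, p = 0.031. At least six are needed.

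The table would detect only a very large excess. Its value is descriptive.

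**The case against.** The strongest reply is that the events the trial is about already have a control. Injuries are AEs under 9.1.3, and injury and post-concussive syndrome are compared worn versus not worn. That stands, and it limits the point to other AEs.

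Next, 9.2 governs collection, and the visit lists may simply abbreviate it. Visits 2 and 3 include a medical history review and examinations, and the withdrawal visit (6.3) follows up adverse events. If 9.2 is followed, the table could be added later without loss. This also stands, which is why the gap is one of planned analysis. It does not remove the mismatch in the lists that staff will use.

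Third, the pilot is small and open label, so a table by period tests nothing and leaves reporting bias in place. Several harms listed in 12.1.2 are also tied in time to deployment, where a background rate adds less. Both are fair and limit the benefit.

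A reader might go further and infer that an event enters the safety analysis only if the unblinded sponsor-investigator attributes it to the device. The documents do not support that. Section 9.1.1 speaks of association with device use and does not require a causal judgement. Section 9.3 ("The Sponsor-Investigator will determine relationship classification") grades every AE and ADE, down to unrelated, and 8.3.3 does not restrict the analysis to events graded as related. Nor can one infer that the trial lacks control data on AEs, because 9.2 requires them in both periods.

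**Conclusion.** The point holds in a limited form. Outside injury and post-concussive syndrome, the plan names only ADEs for the overall safety analysis, and no section plans a rate of other AEs by helmet and no-helmet period. The procedure lists do not match the AE and ADE questioning that 9.2 requires.

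The size is modest. No stated result is wrong, and no bias can be quantified, because the documents give no AE rates. What is lost is a descriptive background rate from about 20 subjects or fewer. The conclusion assumes that 8.3.3 and the secondary endpoint are the full plan for AEs, and that 9.2 is followed in the no-helmet period. If it is not followed, the loss is larger, because the data could not be recovered later. The change is worth making because it is cheap and uses the trial's own randomised comparison.

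**What to change.** 1. In 8.3.3, add a descriptive table of all AEs and SAEs by period of onset (helmet, no helmet). Give the number of subjects with an event and events per person-day, with exact intervals. Use as denominators the subjects who actually entered each period and their days in it. Show relatedness as a secondary column. State that the table is descriptive and that reporting is open label.
2. Align 3.1.2.3, 3.1.2.4, 6.2.1.3, 6.2.1.5, Table 2 and the monthly contact in 7.10 with 9.2, so that AEs and ADEs are both sought in both periods. These places use different terms for the safety review, so each needs its own edit.

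The cost is a wording change and one table from data that 9.2 already requires. The downside is a longer listing that includes unrelated events.

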8.4 Subject Population(s) for Analysis

• All-randomized population: Any subjects in the study, regardless of whether they were assigned to wear the helmet, will be used for any analysis comparing helmet wear vs. no helmet wear.

9 Adverse Device Effects and Adverse Events

9.1 Definitions

9.1.1 Adverse Device Effects

An **adverse device effect (ADE)** is any untoward medical occurrence associated with the use of a device in humans.

9.1.2 Unanticipated adverse device effects (UADEs)

An unanticipated adverse device effect is any ADE that meets at least 1 of the following 3 criteria: 1. Any **serious adverse effect** on health or safety caused by or associated with a device,

In this case, serious adverse effect is defined as any ADE that is:

- fatal
- life-threatening
- requires or prolongs hospital stay
- results in persistent or significant disability or incapacity
- a congenital anomaly or birth defect
- another important medical event

All ADEs that do not meet any of the criteria for serious should be regarded as **non-serious ADEs**.

- 2. Not previously identified in nature, severity, or degree of incidence in the application,
- 3. Any other unanticipated serious problem associated with a device that relates to the rights, safety, or welfare of subjects.

9.1.3 Adverse Event

An **adverse event** (AE) is any symptom, sign, illness or experience that develops or worsens in severity during the course of the study. Intercurrent illnesses or injuries should be regarded as adverse events. Abnormal results of diagnostic procedures are considered to be adverse events if the abnormality:

- results in study withdrawal
- is associated with a serious adverse event
- is associated with clinical signs or symptoms
- leads to additional treatment or to further diagnostic tests
- is considered by the investigator to be of clinical significance

9.1.4 Serious Adverse Event

Serious Adverse Event

Adverse events are classified as serious or non-serious. A **serious adverse event** (SAE) is any AE that is:

- fatal
- life-threatening
- requires or prolongs hospital stay
- · results in persistent or significant disability or incapacity
- a congenital anomaly or birth defect
- an important medical event

All adverse events that do not meet any of the criteria for serious should be regarded as **non-serious adverse events**.

9.1.5 Expectedness

AEs/ADEs must be assessed as to whether they were expected to occur or were unexpected, meaning not anticipated based on current knowledge found in the protocol or product label.

Expected/Anticipated: an AE/ADE known to be associated with the intervention or condition under study.

Unexpected/Unanticipated: an AE/ADE for which the *nature*, *frequency*, or *severity* is not consistent with information about the condition under study or intervention in the protocol, consent form, or product label.

9.2 Recording of Adverse Device Effects and Adverse Events

The study investigator is ultimately responsible for the recording and reporting of AEs, ADEs, and unanticipated problems related to the research, which occur during the study. The study team will collect AE and ADE information from the start of the study (after consent is signed) until the last follow up visit.

At each contact with the subject, a member of the study team will seek information on AEs and ADEs by specific questioning and, as appropriate, by examination. Information on all AEs and ADEs will be recorded immediately in the source document. All clearly related signs, symptoms, and abnormal diagnostic procedures results should be recorded in the source document, though should be grouped under one diagnosis. These AEs and ADEs will be recorded on paper source documents and reviewed by the Principal Investigator and Sponsor designated pharmacovigilance lead (Medical Director).

All AEs and ADEs occurring during the study period will be recorded. The clinical course of each event will be followed until resolution, stabilization, or until it has been determined that the study intervention or participation is not the cause. SAEs and UADEs that are still ongoing at the end of the study period will be followed up to determine the final outcome. Any SAEs and UADEs that occur after the study period and is considered to be possibly related to the study intervention or study participation will be recorded and reported immediately.

9.3 AE/ADE Assessment

The Sponsor-Investigator will determine relationship classification (definitely related, probably related, possibly related, unlikely or unrelated), expectedness (expected or unexpected), and seriousness (serious or non-serious as defined per protocol) of all AEs and ADEs. The relationship of each event will be followed up on until it has been determined that the event is definitely related or definitely not related to the device or participation on the study.

9.4 Investigator Reporting

9.4.1 Reporting to the FDA

Federal Regulation 21 CFR 812.150 dictates mandatory reporting requirements for all IDE and abbreviated IDE studies to the FDA and the IRB. The regulations describe both expedited and annual reporting requirements. Events that do not warrant expedited reporting will be reported at the time of the IDE Annual Report submission to the FDA. Events that require expedited reporting will be reported to the FDA using Form FDA3500A.

Reportable Safety Events				
What Event is Reported	To Whom is Event Reported	When is Event Reported		
Possibly, Probably, or Definitely	Penn IRB	Within 3 days of initial receipt of information		
Related, Unanticipated, & Fatal	FDA	Within 10 days of initial receipt of information		
Possibly, Probably, or Definitely				
Related, Unanticipated, & Serious (Non-Fatal)	FDA	Within 10 days of initial receipt of information		
Possibly, Probably, or Definitely Related, Unanticipated, & Non-Serious	Penn IRB	Within 10 days of initial receipt of information		
Related, Offanticipated, & Nori-Serious	FDA	Annually		
Possibly, Probably, or Definitely	Penn IRB	At continuing review		
Related, Anticipated, & Serious or Non- Serious	FDA	Annually		
Unlikely or Definitely not related,	Penn IRB	N/A		
Anticipated, & Serious or Non-Serious	FDA	Annually		
Unlikely or Definitely not related,	Penn IRB	N/A		
Unanticipated, & Serious or Non-Serious	FDA	Annually		

Other Reportable Events				
What Event is Reported	To Whom is Event Reported	When is Event Reported		
Unapproved protocol deviation to assure	Penn IRB	Within 5 days of initial		
protection of human subjects	FDA	receipt of information		
Use of device without obtaining informed	Penn IRB	Within 5 days of initial		
consent	FDA	receipt of information		
Withdrawal of IRB approval	FDA	Within 5 days of initial receipt of information		
Withdrawal of FDA approval	IRB	Within 5 days of initial receipt of information		
Change in risk by IRB	FDA	Within 5 days of initial receipt of information		
Request by the manufacturer to recall,	Penn IRB	Within 20 days of request		
repair, or dispose device	FDA	Within 30 days of request		

9.4.2 Other Reporting to the Penn IRB

Federal Regulations 21CFR §56.108(b)(1) and 45 CFR 46.103(b)(5) require the IRB to "follow written procedures for ensuring prompt reporting to the IRB...any unanticipated problems involving risk to human subjects or others."

The Office of Human Research Protections (OHRP) considers Unanticipated Problems involving risks to subjects or others, in general, to include any incident, experience, or outcome that meets all of the following criteria:

- Unexpected (in terms of nature, severity, or frequency) given (a) the research procedures that are described in the protocol-related documents, such as the IRB-approved research protocol and informed consent document; and (b) the characteristics of the subject population being studied;
- Related or possibly related to participation in the research (in this guidance document, possibly related means there is a reasonable possibility that the incident, experience, or outcome may have been caused by the procedures involved in the research); and
- Suggests that the research places subjects or others at a greater risk of harm (including physical, psychological, economic, or social harm) than was previously known or recognized.

Other Reportable Events to the IRB		
New information showing increased risk to subjects		
Protocol deviation that places subjects at risk or has the potential to occur again	Within 10 days of initial receipt of information	
Any serious and continuing non-compliance		
Breach of confidentiality		
Incarceration of subject		

All such reportable events will be reported to the IRB per IRB policy.

9.4.3 Follow-up reports

If an SAE/UADE has not resolved at the time of the initial report and new information arises that changes the investigator's assessment of the event, a follow-up report including all relevant new or reassessed information (e.g., concomitant medication, medical history) should be submitted to the IRB and the FDA. The investigator is responsible for ensuring that all SAE/UADEs are followed until either resolved or stable.

9.5 Stopping Rules

In Part 1, if 3/4 of the helmets do not inflate due to a fall from standing in normal controls or dummies, the study will not move on to Part 2.

10 Study Administration, Data Handling and Record Keeping

10.1 Confidentiality

Information about study subjects will be kept confidential and managed according to the requirements of the Health Insurance Portability and Accountability Act of 1996 (HIPAA). Those regulations require a signed subject authorization informing the subject of the following:

- What protected health information (PHI) will be collected from subjects in this study
- Who will have access to that information and why
- Who will use or disclose that information
- The rights of a research subject to revoke their authorization for use of their PHI.

In the event that a subject revokes authorization to collect or use PHI, the investigator, by regulation, retains the ability to use all information collected prior to the revocation of subject authorization. For subjects that have revoked authorization to collect or use PHI, attempts should be made to obtain

permission to collect at least vital status (i.e. that the subject is alive) at the end of their scheduled study period.

10.2 Data Collection and Management

Paper source documents created by the study team will be used to record all subject data. This data will be organized and stored in patient binders located in the locked Clinical Research Office at the Penn Epilepsy Center, Hospital of the University of Pennsylvania, [name]. All CRFs will contain de-identified data, and all medical record printouts will de-identified before being stored in subject binders.

A password-protected excel spreadsheet that links subjects with de-identified data will be stored on the UPHS Neurology shared drive and will only be accessible to the appropriate study staff.

